7.8.2 Sensitivity Analyses

Sensitivity analyses will be performed both on the mITT and ITT populations.

7.8.2.1 Multiple Imputation Assuming Missing at Random

This sensitivity analysis assumes that the diary data are missing at random (MAR), that is, the probability that an observation is missing may depend on the observed values but not the missing values (e.g., the probability of missing Week 5 diary is related to the observed Week 4 or Week 3 value but not the unobserved Week 5 value). In this sensitivity analysis, missing data is imputed multiple times, thus creating the multiply-imputed diary data. The final analysis incorporates the between-imputation variability with the within-imputation variability.

The MI is implemented using the following three steps.

- 1. SAS PROC MI is applied with input dataset containing some missing values for all days during the titration and maintenance period to create 100 datasets. The data sets will include separate columns for the frequency of incidences during each day starting from baseline. The Markov Chain Monte Carlo (MCMC) method will be used to complete the missingness pattern to a monotone pattern separately by treatment arm. The monotone patterns will be achieved by applying sequential imputation based on Bayesian regression with the treatment arm included as a covariate. All copies contain identical values of the non-missing data items, but different values imputed for missing values.
- 2. For each of these MI data sets, the percent change will be computed as in the observed data set and the primary analysis based on the Wilcoxon rank-sum test will be conducted and asymptotic 95% confidence intervals will be constructed.
- 3. To produce a single confidence interval for each dose vs placebo comparison (e.g., Dose 1 versus placebo), PROC MIANALYZE will be used and Rubin's combination rules will be applied to the treatment effect estimates and associated asymptotic standard errors from the MI data sets (Rubin 1987). The treatment effect estimates will be defined as the midpoints of the asymptotic confidence intervals and the standard errors will be defined as the asymptotic standard errors (based on the width of the associated 95% confidence intervals) from the Hodges-Lehmann estimate of the individual datasets.

An example of SAS code is as follows.

PROC MI DATA=adqs NIMPUTE=100 SEED=123456789 OUT=adqs_imp; BY trtp; VAR age sex bwk twk1 twk2 twk3 twk4 twk5; MCMC CHAIN=multiple IMPUTE=full INITIAL=em PRIOR=jeffreys;

RUN;

where trtp is treatment group, bwk, twk1, twk2, twk3, twk4, and twk5 are variables of weekly IA scores during the baseline, and treatment (titration + maintenance) periods. These are derived as (SUM/DAY)*7, where SUM is the total of the IA scores reported on the IA diary in that analysis week, and DAY is the number of days with non-missing IA score in the IA diary in that analysis week. Analysis week is defined as: 1st week is the 1st 7 days after visit 3 (exclusive) during titration, 2nd week is the rest of the days up to Visit 5 (inclusive) in titration period, 3rd week is the 1st 7 days after Visit 5 (exclusive), 4th week is the following 7 days after 3rd week, the 5th week is the rest of the days in maintenance period up to Visit 6 (inclusive). Adqs is the input data set with missing values, and adqs_imp is the complete imputed data set after 100 imputations. For the weekly IA score calculation, if the week has <3 daily diaries, the weekly IA score for this week will be set to missing and imputed using the above procedure.

From the above multiply-imputed IA data, the Hodges-Lehmann confidence interval will be calculated for each imputed data set. The point estimate for the between group difference and the associated standard error (sem) will be derived from the confidence interval. These point estimates and the sem's will be summarized by the SAS MIANALYZE procedure. An example SAS code is as follows.

PROC MIANALYZE DATA=parmest ; MODELEFFECTS estim ; STDERR sem ; ODS OUTPUT PARAMETERESTIMATES=parmest2(KEEP= paramcd label estimate stderr lclmean uclmean probt) ; RUN ;

where estim and sem are the point estimate and standard error from each imputed set, estimate, stderr, lclmean, uclmean, and probt are the final summarized point estimate, standard error, lower and upper confidence limits, and the p-value for the between group comparison (Table 14.2.1.2.1).

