# 6.10 Sample Size and Power Considerations

Based on results from the Phase 2 study, a 15-point average difference in favor of the SPN-810 treatment arms compared with placebo is assumed; the change from baseline to endpoint in total R-MOAS rating was used to evaluate the difference. The R-MOAS was used because there have been no prior studies with the IA diary. A common standard deviation of 34.83 was obtained from a blinded analysis of SPN-810P301 data.

Based on these parameter assumptions, a sample size of approximately 122 per arm will yield 90% power to detect a non-zero difference between the median of SPN-810 treatment and the placebo groups using the Wilcoxon rank-sum test with a 2-sided significance level  $\alpha$ =0.05.

The original sample size of 291 was based on having 3 treatment groups (97 subjects per arm) and specific assumptions on the drug placebo difference, standard deviation and discontinuation rate.

CONFIDENTIAL Version 7.0

[figure not shown]
After the 810P301 study Interim Analysis result was completed, the 18 mg dose arm was discontinued and subjects planned to be randomized to the 18 mg arm would be re-allocated to the 36 mg or placebo arm in a ratio of 2:1. As such there will be an unequal randomization between the 36 mg dose group and placebo. With this post-interim analysis un-equal randomization, the placebo arm is expected to approach approximately 121 subjects of the total of 306 subjects randomized.

The sample size was calculated using the nQuery Advisor Software, Version 7.

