3.5 Determination of Sample Size

The original sample size was based on the results from the Phase 2 study. It was assumed that the average treatment difference between SPN-810 dose groups and placebo is 15 with a common standard deviation (SD) =27.3. A sample size of 77 subjects per arm (1:1:1 allocation ratio) would yield 90% power to detect a non-zero difference between the median of 18 mg or 36 mg dose group and the placebo using the Wilcoxon rank-sum test with a 2-sided significance level of alpha=0.05.

After the interim analysis for Study 810P301, the 18 mg dose arm was discontinued for randomization. Subjects planned to be randomized to the 18 mg arm were re-randomized to the 36 mg or placebo arms at a 2:1 allocation ratio. A blinded review of the 810P301 data indicates that the SD for the interim data was actually 34.83 instead of the protocol assumed 27.3. This new SD leads to a total sample size of 306 (adjusted for 20% attrition) subjects. Approximately 167 subjects were randomized prior to the implementation of the 2:1 randomization. It follows that 139 subjects would be randomized in a 2:1 ratio of 36 mg to following the re-calculation of sample size with the new SD.

The sample size was calculated using the nQuery Advisor Software, Version 7.

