7.8.2.2 Multiple Imputation Assuming Missing Not at Random

This sensitivity analysis assumes that the diary data are missing not at random (MNAR), that is, the probability that an observation is missing may depend on its underlying unobserved value.

This approach may be considered "worst-case" sensitivity analyses as it assumes that after discontinuation subjects from the dosing arms would adopt the outcome model estimated from the placebo arm. To generate missing values from this "placebo-based" imputation model, PROC MI with the MNAR statement will be used (Table 14.2.1.2.2). An example of SAS code is as follows.

PROC MI DATA=adqs NIMPUTE=100 SEED=123456789 OUT=adqs_imp ; CLASS trtp ; VAR age sex bwk twk1 twk2 twk3 twk4 twk5; FCS REG ; MNAR MODEL(bwk twk1 twk2 twk3 twk4 twk5 / MODELOBS=(trtp='PLACEBO')) ; RUN ;

where multivariate imputation is carried out by the fully conditional specification (FCS) method.

Histogram of median percent change from baseline in the frequency of IA Behaviors by imputation status in treatment and maintenance will be created for 36 mg dose and Placebo (Figure 14.2.1.2.1 – Figure 14.2.1.2.2).

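### The MAR imputation section describes two algorithms that cannot both be run, and neither imputation program holds a non-negative diary score at 0 or above

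*SAP*

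**What the plan says.** **Step 1 of SAP 7.8.2.1.** The unit is the day: "The data sets will include separate columns for the frequency of incidences during each day starting from baseline". MCMC is used by arm to make the missing-data pattern monotone. Sequential Bayesian regression with treatment arm as a covariate is then applied. Every completed copy is to carry the observed values unchanged. Protocol 6.9.4.1 contains only this daily, two-stage text.

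**The code in the same section.** It runs by treatment group with "VAR age sex bwk twk1 twk2 twk3 twk4 twk5; MCMC CHAIN=multiple IMPUTE=full INITIAL=em PRIOR=jeffreys". The variables are the baseline week and five treatment weeks. The text after the code defines the five analysis weeks. It adds that for a week with fewer than 3 diaries, "the weekly IA score for this week will be set to missing and imputed using the above procedure".

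**SAP 7.8.2.2, placebo-based analysis.** The text has active-arm children follow the placebo outcome model once they have discontinued. The code uses fully conditional regression with "MNAR MODEL(bwk twk1 twk2 twk3 twk4 twk5 / MODELOBS=(trtp='PLACEBO" as the reference group.

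**The endpoint (SAP 5.1).** PCH_T is 100 x (T - B)/B, where T and B are frequencies per 7 days. A day with no event, confirmed in the evening diary, scores 0, so the score has a floor at 0. Neither program states a bound, transformation or truncation.

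**The concern.** Protocol 6.9.4 names these two analyses as the test of whether the primary result depends on how missing data are handled. Two problems weaken that test.

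- A programmer who follows step 1 and one who follows the code would build different data sets and fit different models. The plan would then not fix the result in advance.
- A normal model on a score with a floor at 0 can draw impossible values. A child whose imputed weeks are negative enough gets a reduction of more than 100%, which the diary cannot produce. Such values would draw questions about the analysis whatever their effect on the estimate.

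The placebo-based program also covers more missing weeks than its text describes, so it is not quite the analysis that the text defines.

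**Working it through.** **1. The plan's own figure.** The imputation sections state no numerical result. The nearest planning figure does reproduce and gives a rough yardstick for step 6. Protocol 6.10 assumes "a 15-point average difference in favor of the SPN-810" arms and says: "A common standard deviation of 34.83 was obtained from a blinded analysis of SPN-810P301 data". With p = Phi(15/(34.83 x sqrt 2)) = 0.6196, Noether's formula gives n = (1.960 + 1.282)^2 / (6 x 0.1196^2) = 122.4 per arm, with power 0.899 at 122. This agrees with "a sample size of approximately 122 per arm will yield 90" percent power. For attrition, 122/0.8 = 152.5, rounded to 153; 2 x 153 = 306, as stated.

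**2. The two recipes side by side (SAP 7.8.2.1).**

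| | Step 1 text | Code and the rules after it |
|---|---|---|
| Unit | Day | Week |
| MCMC | Only to reach a monotone pattern | Imputes everything |
| Second stage | Sequential regression | None |
| Treatment arm | Covariate | BY group, so constant within each run |
| Observed days | Kept unchanged | 1 or 2 diaries in a week are dropped |

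Arm cannot be a covariate where it is constant, and one run cannot be both daily and weekly. The units are not interchangeable. With Visit 5 at 14±2 days and Visit 6 at 21±3 days after Visit 5, week 2 lasts 5 to 9 days (14±2 less 7) and week 5 lasts 4 to 10 days (21±3 less 14). The daily version needs at least 15 + 35 = 50 columns, hence 50 x 51/2 = 1,275 variance and covariance terms per arm, with about 121 placebo children expected (Protocol 6.10).

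**3. Mass below 0.** A normal variable with coefficient of variation CV has Phi(-1/CV) of its mass below 0: 2.3% at CV 0.5, 9.1% at 0.75, 15.9% at 1.0 and 25.3% at 1.5.

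**4. When PCH_T falls below -100%.** Since B > 0, this needs T < 0. One negative week is not enough: the imputed weeks must outweigh all the observed ones. The exposure is therefore mainly among early dropouts.

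**5. Simulation of the quoted MAR code.** Multivariate-normal data augmentation, Jeffreys prior, full imputation within arm, on age, sex, baseline and five weeks. Baseline was at least 6 per week (the mITT floor) and monotone dropout was 20%. The SAP does not say how weeks of unequal length recombine into T, so the five weeks were averaged equally. The distributions are assumptions.

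| Assumed skew (log-SD of baseline) | Imputed weeks < 0 | Children with missing weeks, PCH_T < -100% | Data sets with at least one such child |
|---|---|---|---|
| Mild (0.4) | 7.1% | 0.9% | 24% |
| Moderate (0.7) | 15.5% | 4.3% | 72% |
| Strong (0.9) | 26.9% | 11.8% | 96% |

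A second simulation (mean 28 per week, log-SD 0.4 to 0.9, 20% dropout after week 2, all assumed) gave 5% to 17% negative weeks and 0.2% to 5.5% of imputed children below -100%. The two-arm runs used in step 6 agreed with the table's two middle columns to within 1.5 points. A near-symmetric, low-variance case gave 0.2% negative weeks and no child below -100%.

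**6. Effect on the estimate.** Flooring imputed weeks at 0 moved the Hodges-Lehmann estimate by a mean absolute 0.001 (near-symmetric), 0.06 (mild), 0.7 (moderate) and 0.6 (strong) percentage points. In the second simulation the shift was about 0.1 or less. The planned difference is 15 points, but the protocol takes it from R-MOAS change, so the comparison is loose.

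**7. Reach of the placebo model.** The MNAR statement lists the baseline week and all five treatment weeks and has no condition on discontinuation. An active-arm week on treatment with fewer than 3 diaries is therefore imputed from placebo, which the text does not provide for.

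**The case against.** - *The daily text is leftover wording and the weekly intent is clear.* Largely right. The SAP recasts the protocol's day-based example in weeks, gives weekly rules, supersedes the protocol, and labels its code as an example. That identifies the version to keep. It does not remove step 1, which still prescribes something else.
- *Impossible values are not shown to occur.* This stands. A reader might infer that the programs are bound to produce reductions beyond 100%. The documents give no distribution for IA frequency. Medians and a rank test suggest skew but do not establish it.
- *The effect on the result is small.* This stands too. A reader might infer that dropouts are ranked so favourably that the treatment comparison is distorted. One run under assumed skew did find 14% to 17% of dropouts in the best tenth of responses, against 10% to 12% in the complete data, but this happened in both arms. The rank-based estimate limits extreme values, and step 6 shows shifts below 1 point.
- *There are other checks.* Partly right. The per-protocol analysis (SAP 7.1.4 and 7.8.3) is confined to Visit 6 completers with 80% diary completion, so it is close to a complete-case comparison. It does not vary the assumption about what dropouts would have reported.
- *Applying the placebo model to baseline is harmless.* Agreed. Randomization needs 12 of 15 baseline diaries, so that variable should almost never be missing. On-treatment weeks with fewer than 3 diaries should also be few, but there the code does depart from the text.

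**Conclusion.** The conflict between the two algorithms, and the mismatch between the placebo-based text and code, are established from the SAP alone. The absence of a lower bound is also plain from the code. Its consequence is a possibility whose size rests on assumed distributions: roughly 5% to 27% of imputed weeks negative and about 0.2% to 12% of imputed children below -100% under mild to strong skew, and little or none if the data are near-symmetric. These percentages of children refer to those with imputed weeks, not to the whole arm. They were simulated for the MAR code with the mITT baseline floor; the placebo-based code is open to the same fault because it is also an unbounded linear model.

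The effect on the Hodges-Lehmann estimate is under about 1 percentage point. This is a defect in the specification of two sensitivity analyses that should be corrected. It gives no ground for doubting the primary analysis, which uses no explicit imputation.

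**What to change.** 1. In SAP 7.8.2.1 keep one algorithm: weekly scores, imputed separately by arm, under the existing week definitions and the 3-diary rule. Delete the sentences on daily columns, the monotone step and arm as a covariate.
2. In both programs keep imputed weeks at 0 or above, by predictive mean matching or a stated lower bound of 0. If log(score + 1) is used, also set back-transformed values below 0 to 0: the back-transform exp(z) - 1 is bounded at -1, not at 0.
3. In SAP 7.8.2.2 impute on-treatment gaps under MAR first, then apply the placebo model only to weeks after discontinuation, as the text says.

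The cost is SAP wording and small changes to two programs. No new data are needed.

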Visit 2 will occur at least 15 days prior to Visit 3. Please note that, per protocol and within the EDC, Visit 1 and Visit 2 may occur on the same day.

- 1. Provide training for IA diary and dosing diary module
- 2. Distribute device
- 3. Assess and record concomitant medications

## 4.2.3 Visit 3

Visit 3 will occur at least 15 days following Visit 2 according to the Schedule of Visits and Procedures.

- 1. Administer efficacy scales (SNAP-IV, CHQ-PF28, PSI-4-SF)
- 2. Assess IA diary compliance / review training as necessary
- 3. Confirm eligibility to randomize to study medication treatment
- 4. Randomize subject via IWRS
- 5. Administer Investigator CGI-S
- 6. Administer Infrequent Behaviors Checklist
- 7. Administer safety scales (Simpson-Angus, Barnes Akathisia, AIMS)

Supernus® Pharmaceuticals, Inc. 810P302

- 8. Record height, weight, and BMI
- 9. Collect blood samples for hematology/chemistry
- 10. Collect urine samples for urinalysis, urine drug screen (all subjects), and pregnancy test (FOCBP only)
- 11. Administer C-SSRS
- 12. Record concomitant medication
- 13. Assess for any clinically significant change in Medical History
- 14. Dispense SM via IWRS.
- 15. Review training on dosing diary module
- 16. Assess adverse events (post-dose)

#### 4.2.4 Visit 4

Visit 4 will occur 7 (±2) days following Visit 3 according to the Schedule of Visits and Procedures.

- 1. Administer Investigator CGI-S
- 2. Administer caregiver and investigator-completed CGI-I
- 3. Administer Infrequent Behaviors Checklist
- 4. Administer safety scales (Simpson-Angus, Barnes Akathisia, AIMS)
- 5. Record height, weight, and BMI
- 6. Perform 12-lead ECG
- 7. Collect blood samples for PK analysis
- 8. Administer C-SSRS
- 9. Record concomitant medication
- 10. Review IA diary compliance and provide training as required
- 11. Collect AEs
- 12. Review dosing diary compliance and provide training as required

## 4.2.5 Visit 5

Visit 5 will occur 14 (±2) days following Visit 3 according to the Schedule of Visits and Procedures.

- 1. Administer Investigator CGI-S
- 2. Administer caregiver and investigator-completed CGI-I
- 3. Administer Infrequent Behaviors Checklist
- 4. Administer safety scales (Simpson-Angus, Barnes Akathisia, AIMS)
- 5. Record height, weight, and BMI
- 6. Collect blood samples for PK analysis
- 7. Administer C-SSRS
- 8. Record concomitant medication
- 9. Review IA diary compliance and provide training as required
- 10. Collect AEs

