- 11. Collect returned SM; assess treatment compliance
- 12. Review dosing diary compliance and provide training as required
- 13. Dispense SM

## 4.2.6 Visit 6

Visit 6 will occur 21 (±3) days following Visit 5 according to the Schedule of Visits and Procedures.

- 1. Administer efficacy scales (Investigator CGI-S, caregiver and investigator CGI-I, SNAP-IV, CHQ-PF28, PSI-4-SF)
- 2. Administer Infrequent Behaviors Checklist
- 3. Administer safety scales (Simpson-Angus, Barnes Akathisia, AIMS)
- 4. Record height, weight, and BMI
- 5. Perform 12-lead ECG
- 6. Perform physical examination
- 7. Collect blood samples for hematology/chemistry
- 8. Collect urine sample for urinalysis
- 9. Administer C-SSRS
- 10. Record concomitant medication
- 11. Review IA diary compliance and provide training as required
- 12. Collect AEs
- 13. Collect returned SM; assess treatment compliance
- 14. Review dosing diary compliance and provide training as required
- 15. Determine whether subject wishes to participate in open-label extension
- 16. Dispense SM (either Conversion or Taper based upon subject's decision about participation in open-label extension)

## 4.2.7 Visit 7

Visit 7 will occur 7 (±1) days following Visit 6 according to the Schedule of Visits and Procedures. These procedures will also be performed for patients who discontinue early. Patients who discontinue early after Visit 5 will be offered a taper kit.

- 1. Administer safety scales (Simpson-Angus, Barnes Akathisia, AIMS)
- 2. Record vital signs (HR, BP, temperature, and RR), height, weight and BMI
- 3. Collect urine sample for pregnancy test (FOCBP only)
- 4. Administer C-SSRS
- 5. Record concomitant medication
- 6. Collect AEs
- 7. Collect SM and assess treatment compliance
- 8. Collect device
- 9. Complete/discontinue subject
- 10. Collect blood samples for hematology/chemistry
- 11. Collect urine sample for urinalysis

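### SAP 7.8.2.1 sets weeks with one or two diaries to missing, so both imputation analyses discard recorded days, often the last ones before dropout

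*SAP*

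**What the plan says.** SAP 7.8.2.1 describes the imputation in two ways.

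- Its numbered steps work by day: "The data sets will include separate columns for the frequency of incidences during each day starting from baseline". They add: "All copies contain identical values of the non-missing data items, but different values imputed for missing values". Step 2 then derives percent change in the same way as for the observed data. Protocol 6.9.4.1 gives the same daily description and has no minimum number of diaries.
- The text after the example code works by week. Weekly scores are (SUM/DAY)*7, and "if the week has <3 daily diaries, the weekly IA score for this week will be set to missing and imputed". The week in which a child discontinues is not excepted.

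SAP 7.8.2.2 does not restate the rule, but its code reads the same input data set and the same weekly variables: "MNAR MODEL(bwk twk1 twk2 twk3 twk4 twk5 / MODELOBS=(trtp='PLACEBO". Its stated assumption is that "after discontinuation subjects from the dosing arms would adopt the outcome model estimated from the placebo arm".

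The primary analysis (SAP 5.1 and 6.4) averages over all days with a non-missing diary and sets no minimum. The maintenance-only analysis in SAP 7.8.2.3 does not use the weekly scores.

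**The concern.** A week with one or two diaries contains data. Setting it to missing replaces those recorded days with model draws, although step 1 says observed values do not change. With good compliance, such a week is usually the partial week in which a child leaves. The two analyses meant to test whether dropout is informative would then drop the observations closest to it, while the primary analysis keeps them. For a child whose aggression worsened just before leaving, the sensitivity result could look better than the primary one.

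The threshold has a second side. A dropout week with three to six diaries counts as fully observed, so the rest of that week keeps the on-treatment rate even in the placebo-based analysis.

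**Working it through.** **The plan's own figures.** The rule carries no figure. The check borrows 20% attrition and N = 306 from SAP 3.5. These reproduce: p = Φ(15/(34.83 × √2)) = 0.6196; n = (1.960 + 1.282)²/(6 × 0.1196²) ≈ 122 per arm, as in Protocol 6.10; 122/0.80 = 152.5, rounded up to 153, and 2 × 153 = 306. Expected dropouts: 0.20 × 306 ≈ 61.

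**How often the rule bites.** SAP 7.8.2.1 defines the weeks: "3rd week is the 1st 7 days after Visit 5 (exclusive), 4th week is the following 7 days after 3rd week". Week 1 is also 7 days; weeks 2 and 5 take what is left of their periods. Protocol 4.2.5 and 4.2.6 give the windows: "Visit 5 will occur 14 (±2) days following Visit 3" and "Visit 6 will occur 21 (±3) days following Visit 5". Assume that the last diary day is equally likely to be any of 35 days and that diaries are complete until then.

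- Last days 1, 2, 8, 9, 15, 16, 22, 23, 29 and 30 leave one or two diaries in the final week: 10/35 = 28.6% (10/34 = 29.4% if day 35 counts as completion). That is about 17 of 61 dropouts, or about 6% of children (0.29 × 0.20).
- Treatment can last 30 to 40 days within the windows: 10/30 = 33% to 10/40 = 25%.
- If each diary is completed with probability 0.8, the share is 36% (31-42% across the windows).
- Two of the ten days fall in week 1. So 2/35 = 5.7% of dropouts lose all post-baseline diary data, although one assessment admits them to the ITT population (SAP 7.1.3).

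**One child, late relapse.** Baseline 14/week, weeks 1-3 at 7/week, then two diaries of 10 behaviours each, then dropout. Imputed weeks are held at 7/week, and the period value is the mean of five 7-day weeks.

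- Primary: T = (21 + 20)/23 × 7 = 12.48; 100 × (12.48 - 14)/14 = -11%.
- Under the rule: T = (7 + 7 + 7 + 7 + 7)/5 = 7; -50%.
- Observed days kept: week 4 = 20 + (5/7) × 7 = 25; T = (21 + 25 + 7)/5 = 10.6; -24%.
- With a milder relapse of 4 per day, the three values are -37%, -50% and -41%.

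**Can the sign change?** Baseline 20/week, week 1 at 16 (-20%), then two diaries of 6 each. The primary value is T = (16 + 12)/9 × 7 = 21.8, or +9%. The imputation analyses see only the week at -20%. For the primary value to be positive, the last two days must run at 1.7 times the baseline rate (dropout in week 2 after -20%), 2.75 times (week 2 after -50%), 4.5 times (week 3 after -50%) or 8 times (week 5 after -50%).

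**Treatment comparison.** A small simulation took 185 (306 - 121) on 36 mg against 121 on placebo, 20% dropout, and relapse at 2 to 4 times baseline in affected dropouts. If both arms relapse alike, deleting the days moves the Hodges-Lehmann difference by at most 0.2 points. If only affected 36 mg dropouts relapse, it moves from about -12.0 to -14.5 (2 times) or -11.6 to -14.9 (4 times), a shift of about 2.5 to 3.3 points towards the drug.

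**Weeks with three to six diaries.** Of last days 1-34, 20/34 = 59% leave such a week, with 4, 3, 2 or 1 days unimputed. The mean over all dropouts is 5 × (4 + 3 + 2 + 1)/34 = 1.5 days, out of a mean of 17.5 post-dropout days.

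**The case against.** The strongest reply is that the steps describe daily columns and the code is only an example, so a daily implementation would keep every observed day. That is correct, but it confirms that the section specifies two procedures, and the less-than-three rule stands in the text, not in the code. The non-missing items in step 1 could also be read as the non-missing weekly inputs to the procedure. That removes one contradiction, not the conflict with the daily columns or with the primary analysis.

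A minimum-diary rule has a purpose: it avoids multiplying one or two days by 7 or 3.5 to make a week. That stands, and it justifies a threshold for fitting the model, not for discarding data.

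A reader might infer that the rule generally turns a recorded relapse into an improvement. The late-relapse record does not show this: all three of its values are improvements. Part of its gap (-11% to -24%) arises because the primary analysis extends the last days over the remaining time, and keeping the observed days does not remove that part. No value has been worked out for the placebo-based draws, so -50% applies only with imputed weeks held at 7/week.

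A reader might also infer bias in favour of the drug. The rule applies to both arms and deletes late improvement as readily as relapse. The documents give no dropout timing, and the discontinuation reasons in SAP 7.3 have no separate category for worsening.

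**Conclusion.** The concern holds in limited form. SAP 7.8.2.1 contradicts itself, and followed as written both imputation analyses discard recorded diary days, often those nearest dropout. The primary analysis and the maintenance-only analysis are untouched by the rule.

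About 29% of dropouts would be affected under uniform dropout and complete diaries, and roughly 25-42% across the visit windows and 80-100% compliance: a sizeable minority. For an affected child with a late relapse, the imputed percent change can be clearly more favourable than the primary. A change of sign over the whole period is realistic mainly for early dropouts.

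The treatment comparison shifts materially only if change before dropout differs by arm. Nothing in the documents shows that it will, but these analyses exist to probe that possibility, so symmetry should not be built in by deleting the evidence. The simulated shift depends on the assumed relapse and shows direction and order of size only. The second side of the threshold is a real inconsistency with SAP 7.8.2.2, but a small one; the 59% share overstates it.

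**What to change.** Reconcile the daily and weekly descriptions in SAP 7.8.2.1 so that every observed diary day stays in each imputed data set at its actual count and only unobserved days are imputed:

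- weekly total = observed SUM + (unobserved days / days in that week) × imputed weekly rate;
- T = (sum of weekly totals / total days) × 7.

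A minimum-diary threshold may remain, stated as applying only to fitting the weekly imputation model. In SAP 7.8.2.2, apply the placebo model to all days after discontinuation, including the rest of the dropout week.

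The cost is minor SAP wording and programming. No new data are needed and the primary analysis does not change.
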